## 4:1 Primary objective

The primary objective is to compare the change in SOFA-score (Appendix 8:2) on day 7 of ICU stay as compared to the day starting nutritional treatment and glutamine supplementation. Only patients who have received glutamine for not less than 3 days will be considered.

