## 8. Efficacy assessment

Each day of the study following things will be performed:

a) study drug (glutamine or placebo) will be given intravenously during 12 h.

b) volume of infused solution and time interval of infusion will be registered.

c) total amount of nutrition during 24 h will be recorded.

d) SOFA score will be calculated.

End of ICU-stay will be recorded and as well as the route of discharge. If the patient is moved to another intensive care unit, the patient leaves the study. Still if the patient is treated more than 3 days, he is included and evaluated in the study although the ICU-stay is prolonged in another unit and patient during that time does not receive any controlled treatment. Provision of nutrition after ICU-stay (or after readmission to ICU) will not be recorded. If patient is readmitted to ICU within 24 h study protocol is continued. If patient is readmitted to ICU after more than 24 h the patient will not be included. Patient will not be included again in the study and the second (or consecutive) stay will not be recorded as ICU-stay in the protocol.

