#### **10. Statistics**

The study is designed with one primary endpoint as the primary objective and several secondary endpoints as secondary objective. The statistical power calculation to determine the sample size is performed for the primary endpoint. Parametric and non-parametric statistics will be used depending on whether the parameters are normally distributed or not. As 3 days of treatment is an inclusion criteria all calculation will be made on included as well as randomised patients (intention to treat)

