## 10:6 Subject classification

All patients who are eligible for the study are registered and if they are not randomised the reason is noted. All patients that are randomised are registered as randomised and as included if treatment is started. For patients who are randomised but not included the reason is noted. Patients who are randomised and have received treatment will be classified as withdrawals. Patients may withdraw from the trial at their own request or at the discretion of the investigator. Patients treated for less than 3 days (3 treatment periods) will also be classified as withdrawals. Patients with failure of treatment on two consecutive days will also be withdrawn from the study. A minimum of 3 treatment periods on consecutive days will be necessary for evaluation. Analyses of the results will be made on the basis of included patients as well as on the basis of "intention to treat" and "screened patients". "Intention to treat" meaning all patients randomised, including those not given 3 days of treatment depending upon death, discharge or discontinuation of other reasons. "Screened patients" meaning all patients possible to include.

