### 10:7 Drop-outs and Missing Data

Drop-outs before day 7 of ICU stay will be considered as withdrawals. Drop-outs after that day will be evaluated in the primary outcome variable, and the same goes for day 10. For evaluation in length of stay and mortality, drop-out will be considered as withdrawals. Missing data will be considered as non-existent.

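### The primary SOFA comparison is limited to patients treated for at least 3 days, a condition known only after randomisation, against the promised intention-to-treat analysis; and 10:7 is not reconciled with 8:1

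*Protocol*

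**What the plan says.** **Restricting the population.** Section 4:1 says of the primary SOFA comparison: "Only patients who have received glutamine for not less than 3 days will be considered". Section 10:6 classes patients with fewer than 3 treatment periods as withdrawals and adds: "A minimum of 3 treatment periods on consecutive days will be necessary for evaluation".

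**Promising intention to treat.** Section 10 opens its rule with "As 3 days of treatment is an inclusion criteria" and continues that "all calculation will be made on included as well as randomised patients (intention to treat"). Section 10:6 defines intention to treat as everyone randomised, including those who fell short of 3 days because they died, were discharged or stopped for another reason. It lists three bases for analysis (included, intention to treat, screened) and ranks none of them.

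**Drop-outs.** Section 10:7 states: "Drop-outs before day 7 of ICU stay will be considered as withdrawals". Later drop-outs are evaluated for the primary outcome. For length of stay and mortality, drop-outs are again withdrawals. Section 10:2 takes 6-month mortality from the public register.

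**Early death and discharge.** Section 8:1 keeps patients who die or are discharged before day 7 by using the SOFA score of that day. The form in 19:4 records drop-out (consent withdrawn, failed drug administration, other) separately from route of discharge, which includes death.

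**The concern.** Three days of treatment is treated as an entry criterion, but it is something that happens, or does not, after allocation. In an ICU trial whose purpose (section 4) is the effect on morbidity and mortality, early death and early recovery are among the outcomes under study. A primary comparison conditional on lasting 3 days of treatment compares two groups that randomisation did not form. If glutamine changes who dies, recovers or stops early, the retained groups can differ even where the full arms do not.

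The same uncertainty reaches the interim calculation after 500 patients (10:1 and 13). It uses the primary endpoint and leads to a decision whether to continue, so it too needs one stated population.

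The drop-out rule adds a second filter, at day 7, whose overlap with 8:1 is not explained. For mortality it sets patients aside although their vital status can be had from a register.

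**Working it through.** **1. Can the 3-day condition be an inclusion criterion?** Section 6:2 lists ICU admission, a decision to give full nutrition, APACHE II above 10 and age 18 to 85. Treatment duration is absent. Section 6:5 allows randomisation only when all inclusion criteria are met, which is impossible for a condition settled days later. Section 10:6 also registers a randomised patient as included once treatment starts, so the word has two meanings.

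**2. Can 4:1 and 10 both hold?** Section 4:1 admits only the 3-day patients to the primary comparison. Sections 10 and 10:6 run every calculation on all randomised patients as well. A patient who dies on treatment day 2 is out under 4:1 and in under 10:6.

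**3. Is the filter one rule?** It is at least 3 days in 4:1 and 3 consecutive periods in 10:6. In section 8, on transfers to another ICU, it reads "if the patient is treated more than 3 days, he is included and evaluated in the study". A transferred patient with exactly 3 days is in under one wording and out under another. Read literally, 4:1 also asks for glutamine, which the placebo arm never receives.

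**4. 8:1 beside 10:7.** If drop-out means the reasons on the 19:4 form, the two sections cover different patients and do not conflict. If it means anyone who leaves before day 7, they contradict each other. Section 10:7 does not say which.

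**5. Scale for the illustration.** Section 10:3 gives 0.75 points, 80% power and about 500 per group, but no SD or significance level, so 500 cannot be reproduced. Solving for the SD at two-sided 0.05:

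SD = 0.75 / [(1.960 + 0.842) × √(2/500)] = 0.75 / 0.1772 = 4.23.

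One-sided 0.05 gives 4.77; two-sided 0.025 gives 3.85. I use 4.23.

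**6. Possible bias.** Assume no difference between the full arms, excluded shares e_P (placebo) and e_A (active), and excluded patients whose mean SOFA change is g points worse than the overall mean. The retained mean shifts by −g·e/(1−e), so

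bias = −g × [e_A/(1−e_A) − e_P/(1−e_P)].

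For 10% vs 15% and g = 4: −4 × (0.1765 − 0.1111) = −0.26. The standard error is 4.23 × √(1/450 + 1/425) = 0.286, so the shift is 0.91 standard errors. Two-sided type I error is then Φ(−1.96 + 0.91) + Φ(−1.96 − 0.91), about 15%.

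| Excluded, placebo vs active | Bias (g = 4) | Type I error |
|---|---|---|
| 10% vs 10% | 0 | 5% |
| 10% vs 12% | −0.10 | about 6.5% |
| 10% vs 15% | −0.26 | about 15% |
| 20% vs 25% | −0.33 | about 20% |

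With g from 2 to 6, 10% vs 15% gives −0.13 to −0.39 points and type I error of 7% to 28%. If the excluded patients are mainly early recoveries, g is negative and the sign reverses. All shares and values of g are assumptions.

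**7. Price of intention to treat.** If a share d is briefly treated and gains nothing, the difference becomes 0.75 × (1−d). Power with 500 per arm is Φ[0.75(1−d)/0.2677 − 1.96], where 0.2677 = 4.23 × √(2/500):

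- d = 10%: 0.675/0.2677 = 2.52, power 71%
- d = 20%: 0.600/0.2677 = 2.24, power 61%
- d = 30%: 0.525/0.2677 = 1.96, power 50%

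**The case against.** Intention to treat is not missing. It is promised in 10 and defined properly in 10:6. A reader might infer from 4:1 that early deaths vanish from the results. The documents do not support that: those patients stay in the intention-to-treat analysis, 9:2 reports every death among randomised patients as a serious adverse event, and 8:2 records ICU and 6-month mortality. They are lost only from the 3-day set.

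A reader might also infer that 10:7 discards everyone who leaves before day 7. Section 8:1 keeps deaths and discharges, and 19:4 treats drop-out as a separate category. What stands is that 10:7 does not state the relation, and that a death or discharge before 3 periods still takes the patient out of the set in 4:1.

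The trial is double-blind, which makes unequal exclusion less likely. That is a fair limit on the concern, but blinding does not stop the drug itself from affecting death, recovery or discharge.

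A statistical analysis plan, not shown, might rank the sets, and 6:5 locks the randomisation list until clean file. So I do not claim that the deciding set would be picked after unblinding. A later plan would still have to overrule either 4:1 or 10.

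Finally, power does not favour the change: step 7 shows that dilution can be costly. Nor can a loss of power from the exclusions be asserted, since 6:5 provides reserve subjects and section 5 can be read as 1,000 patients with at least 3 days of treatment.

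**Conclusion.** The point holds as a contradiction with a possible bias. The primary objective is tied to a subset formed after randomisation by events that 10:6 itself names, while 10 and 10:6 promise the full randomised comparison and nothing says which decides. This rests on the text alone and needs no assumed figure.

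Whether bias arises depends on the arms. There is none if exclusions are equal in number and alike in kind. With modest imbalance it could be a third or more of the 0.75-point target (0.26/0.75 = 35% at 10% vs 15% and g = 4). That range rests on assumed shares, an assumed gap and an SD back-solved at two-sided 0.05. To say that the randomised comparison is necessarily broken would go further than the documents allow.

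The drop-out rule is a separate and smaller fault: an unexplained relation to 8:1, and no good reason to set drop-outs aside for a mortality endpoint read from a register. The population for the primary endpoint must be settled before the trial is analysed, including at the interim look.

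**What to change.** - **4:1, 10 and 10:6:** name all randomised patients, by assigned arm, as the primary analysis set for the SOFA change. Stop calling 3 days of treatment an inclusion criterion.
- **Supportive set:** keep one, defined once as 3 or more treatment periods of study drug (not glutamine), and use the same wording in the Summary, 4:1, 8 and 10:6.
- **10:7:** state that deaths and discharges before day 7 follow 8:1. State that drop-outs stay in the primary analysis with the SOFA scores recorded while they are in the ICU, as far as consent allows. Analyse register mortality for all randomised patients where consent allows.
- **10:6, two corrections:** the sentence "Patients who are randomised and have received treatment will be classified as withdrawals" appears to have lost a 'not'; as printed it makes every treated patient a withdrawal. Use screened patients to describe patient flow only, since those not randomised have no arm to compare.

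**Cost.** Mostly wording. The daily tasks in section 8 cover days in the study, so SOFA recording would have to continue to day 7 for consenting drop-outs still in the ICU. The real downside is dilution, which can be material (step 7: power of 71%, 61% or 50% under the stated assumptions). The sample size should be looked at again once an expected share of briefly treated patients is available.

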#### 6:2 Inclusion criteria

Subjects will be enrolled in the trial when they meet the following criteria:

- a) admission to the ICU
- b) decision to give the patient full nutrition
- c) APACHE II score >10 at admission
- d) age 18-85 years

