#### 6:5 Randomisation

Subjects will be randomised to treatment only if they satisfy all inclusion criteria. The trial will include 500 subjects in each treatment group. Block randomisation means that the subjects will be assigned randomly to active or placebo treatment with equal size of the two treatment groups at each investigational centre. A computer program using the method of random allocation within fixed blocks will generate a randomisation list. It will provided for a defined number of subjects and a defined number of reserve subjects at each investigational centre. The randomisation list will be securely locked away during the trial by the responsible statistician until clean file has been declared.

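### The primary comparison is confined to patients who went on to receive at least 3 days of study treatment, and the protocol does not say whether this set or all randomised patients decides the result

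*Protocol*

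**What the plan says.** Section 4:1 defines the primary objective as the change in SOFA score from the start of treatment to ICU day 7, and adds: "Only patients who have received glutamine for not less than 3 days will be considered". Section 10:6 supports this restriction twice: "Patients treated for less than 3 days (3 treatment periods) will also be classified as withdrawals", and "A minimum of 3 treatment periods on consecutive days will be necessary for evaluation".

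The 3-day condition is not an entry criterion. Section 6:5 says: "Subjects will be randomised to treatment only if they satisfy all inclusion criteria". The criteria in 6:2 are ICU admission, the "decision to give the patient full nutrition", APACHE II above 10 and age 18-85. Section 10 nevertheless treats the condition as one, and in the same sentence asks for two analyses: "As 3 days of treatment is an inclusion criteria all calculation will be made on included as well as randomised patients (intention to treat". Section 10:6 lists three sets side by side. It begins "Analyses of the results will be made on the basis of included patients as well as on the basis of" and goes on to intention to treat and screened patients. It defines intention to treat as everyone randomised, including those who missed 3 days through death, discharge or other discontinuation.

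Two further rules bear on who is counted. Section 8:1 keeps patients who die or are discharged before day 7 by substituting the SOFA score of that day. Section 10:7 says: "Drop-outs before day 7 of ICU stay will be considered as withdrawals". Sections 10:1 and 13 plan an interim look at the primary endpoint at 500 patients and name no analysis set for it.

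**The concern.** Randomisation makes the two arms comparable at entry. A filter applied three treatment days later keeps them comparable only if treatment has no influence on who passes it. Here the filter works through death, discharge and discontinuation, in a trial whose stated purpose is to find an effect on morbidity and mortality. If glutamine averts some early deaths, the sick patients it saves enter the active arm's 3-day set and worsen its SOFA change. If it hastens early deaths, those patients leave the set and the active arm looks better. Blinding stops staff from selecting by arm, but it does not stop selection caused by the drug.

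The second problem is that the deciding set is unclear. Section 4:1 points to the 3-day set alone, while sections 10 and 10:6 put the all-randomised set beside it. If the two disagree, at the interim look or at the end, the protocol gives no answer.

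**Working it through.** **Order of events.** Patients are randomised on the 6:2 criteria, which contain no 3-day condition. Treatment follows, and the third treatment period comes at the earliest on the third day. The restriction in 4:1 therefore acts after randomisation, whatever section 10 calls it. The term for included patients also has two senses: treatment started (10:6) and 3 days treated (10).

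**Who is lost.** Under 4:1 and 10:6, the deaths and discharges lost are those before 3 treatment periods. Later ones before day 7 stay in through 8:1.

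**The protocol's own figure.** Inputs from 10:3 are a difference of 0.75, 80% power and about 500 per group. The protocol gives no SD or significance level, so 500 cannot be reproduced independently. Assuming two-sided 5%, the SD that yields it is

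SD = 0.75 / [(1.960 + 0.842) × √(2/500)] = 4.23.

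**Bias of the 3-day comparison.** Assumptions, none from the protocol:
- q, the share under 3 days in the arm with more early deaths, is 15% or 25%.
- δ, the difference in early death between arms, is 1, 3 or 5 percentage points.
- The extra survivors have a SOFA change 5 points worse than the rest.
- Treatment has no effect on SOFA change in the other patients.

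The arm with fewer early deaths keeps a share 1 − q + δ, of which δ are the extra patients. So bias = 5δ / (1 − q + δ). With n = 500(1 − q) per arm, n is 425 or 375 and the standard error 4.23 × √(2/n) is 0.290 or 0.309.

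| δ | Bias, q = 15% | Bias, q = 25% | Share of 0.75 | Rejection rate at nominal 5% |
|---|---|---|---|---|
| 1 point | 0.05/0.86 = 0.06 | 0.05/0.76 = 0.07 | 8-9% | about 5.5% |
| 3 points | 0.15/0.88 = 0.17 | 0.15/0.78 = 0.19 | 23-26% | 9.0-9.5% |
| 5 points | 0.25/0.90 = 0.28 | 0.25/0.80 = 0.31 | 37-42% | 16-17% |

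A second set-up gives the same order of size. Let there be no effect in all randomised patients, early-exit shares of 10% and 15%, and excluded patients who differ from the overall mean by D. Then bias = D × (0.15/0.85 − 0.10/0.90) = 0.065 × D, which is 0.13, 0.26 or 0.39 points for D = 2, 4 or 6. With equal shares and equally ill excluded patients, the bias is 0 in both set-ups.

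**If 4:1 does not govern.** Suppose success could be claimed on either set. With a share s of patients outside the 3-day set, the two test statistics correlate at about √(1 − s). The chance that at least one is significant under no effect is 6.5%, 7.1% or 7.6% for s = 10%, 20% or 30%. This is an alternative to the bias scenario and must not be added to it.

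**Power of each set**, with 500 randomised per group, SD 4.23 and two-sided 5%. The all-randomised column takes the unfavourable case that short-treated patients gain nothing, so the effect is 0.75(1 − d). The 3-day column keeps 0.75 but has 500(1 − d) patients per group.

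| Short-treated, d | All randomised | 3-day set |
|---|---|---|
| 10% | 71% | 76% |
| 15% | 66% | 73% |
| 20% | 61% | 71% |
| 25% | 56% | 68% |

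**The case against.** The best defence is that the protocol already requires the all-randomised analysis, twice, and defines it properly. Early deaths and discharges are thus lost from one analysis and not from the trial, and a statistical analysis plan could rank the sets. The first part stands. The second helps less, because the protocol has not left the choice open. Section 4:1 makes one, and a plan naming all randomised patients would contradict it.

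The size is also open to challenge. A difference of 3-5 percentage points in death within three treatment days is a large effect, and section 10:3 itself expects only a limited effect from a short treatment period. At 1 point the distortion is small. That stands, which is why the range starts there.

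Three stronger readings are tempting, and the document does not support them:
- A reader might infer that all deaths and discharges before day 7 leave the comparison. Section 8:1 keeps them once 3 treatment periods are completed. The report form in 19:4 lists death and discharge routes apart from drop-out, so 10:7 is most naturally read as covering other drop-outs only.
- A reader might infer that success may be claimed on either set. Nothing says so. The 6.5-7.6% applies only if 4:1 does not govern.
- A reader might infer that 4:1 drops the placebo arm because it speaks only of glutamine. Sections 5 and 7 give the 3-day minimum for glutamine or placebo, so this is loose wording.

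**Conclusion.** The point holds. Section 4:1 selects the primary population on something that happens after randomisation and is linked to outcome. It also conflicts with sections 10 and 10:6, which require all randomised patients without a ranking. Both the restriction and the contradiction are plain from the text and rest on no assumption.

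The size does rest on assumptions: the early-exit share, the difference in early death, the 5-point gap and an SD inferred from the sample size. Within the range shown, the bias runs from negligible to about two fifths of the target difference. The rejection rates refer to no effect on SOFA change in the other patients. They are not a null of no drug effect at all, since early death is assumed to differ. The calculation does not show that the trial's result would be biased, only that the design does not protect against it. The correction is needed because it settles who counts in the primary comparison and in the interim decision.

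**What to change.** - In 4:1, 10 and 10:6, state that all randomised patients, in the arm to which they were randomised, are the sole set for the primary endpoint and the interim decision.
- Make the analyses of patients with at least 3 treatment periods and of screened patients supportive, with no claim of their own.
- Define included patients once and use the term in that sense throughout. Stop describing 3 days of treatment as an inclusion criterion.
- Reconcile 10:7 with 8:1. Deaths and discharges before day 7 stay in through the 8:1 substitution. Other drop-outs before day 7 stay in the primary analysis, with a stated rule for their day-7 value, instead of being removed as withdrawals. Such a rule is needed because 8:1 covers only death and discharge, and 10:7 treats missing data as if they did not exist.
- Restate the power in 10:3 for the chosen set, giving the SD, the significance level and the expected short-treated share.

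The wording changes are cheap, since 10:6 already requires the intention-to-treat analysis. The real cost is power. If short-treated patients gain nothing, restoring 80% takes 500/(1 − d)² per group: about 618, 693, 782 or 889 at 10%, 15%, 20% or 25% short-treated. If they gain something, the need is smaller. Keeping the 3-day set would not avoid the problem, because it also falls below 80% at 500 randomised per group.

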## 4:2 Secondary objectives

The ICU mortality, the 6-months mortality, the length of ICU stay and the change in SOFAscore on day 10 of ICU stay as compared to the day starting nutritional treatment and glutamine supplementation will also be calculated.

## 5. Trial design

This trial is designed as a prospective block-randomised, double-blinded, placebo-controlled multi-center trial in the Scandinavian countries. A total of 1.000 ICU-patients will receive a daily support of glutamine or placebo-treatment (NaCl) during on at least 3 consecutive days.

